4.5.3 FACIT GP5

A single PRO questionnaire that can inform the overall tolerability of a dose from Functional Assessment of Cancer Therapy- item GP5 (FACIT- item GP5) will be collected.

4.5.4 PoM Biomarker

The pharmacodynamic effect of DZD9008 on PoM biomarkers in tumor tissue from paired biopsies will be evaluated. The biomarker study will include, but not limit to pEGFR. Percent change from baseline in pEGFR will be derived for analysis purpose.

[figure not shown]
5. STATISTICAL METHODS

5.1 General Principles

All data processing, summarization and analyses will be performed using SAS® 9.4 (or higher) in Dizal Data Warehouse.

The data in part B of study will be analysed and reported by treatment group (dose), unless otherwise specified.

Unless otherwise specified, the typical descriptive statistics for continuous variables will include number of patients (n), mean, standard deviation (SD), median, minimum (min), and maximum (max) values. Categorical variables will be summarized by presenting the number and percentage of patients in each category.

5.2 Patient Disposition and Analysis Sets

Patient disposition will be summarized by treatment group and overall in SS and will include the number and percentage of patients:

- Treated;
- Treatment status (ongoing, discontinued);
- Study Status (Remained on study, completed, or discontinued);

In addition, for the patients who discontinued the treatment or who discontinued from the study, a breakdown of the primary reasons for discontinuation will be presented.

The number and percentage of patients included in each analysis set (SS, FAS, PKS) will also be reported in SS.

The number of patients screened but not treated as well as a summary of the reasons for screen failure will be produced, based on all patients.

The patient disposition data for patients who discontinued from treatment or study will be listed in the individual data listing. The treated patients excluded from any analysis set will also be listed, with the reason for exclusion.

5.3 Protocol Deviation

All important protocol deviations will summarized by treatment group and overall in SS, number and percentage of patients with each category of deviations will be reported. If applicable, the protocol deviations related to coronavirus disease 2019 (COVID-19) will be reported separately. All important protocol deviations will be presented in the individual data listing.

5.4 Demographic and other Baseline Characteristics

Unless otherwise specified, the demographic and other baseline characteristics in this section will be analyzed and reported in SS. If 10% or higher difference in number of patients is observed between analysis sets, the tables will be repeated in FAS, as applicable.

5.4.1 Demographic and other Data at Baseline

Demographic and baseline characteristics will be listed and summarized by treatment group and overall in analysis set(s) applicable. Standard descriptive statistics will be presented for the continuous variables below:

- age (years);
- weight (kg) at baseline;
- height (cm) at baseline;
- baseline body mass index (BMI) in kg/m², calculated as (weight/height²) where weight is in kg and height is in m;

The number and percentages of patients will be presented for the categorical variables below:

- age group (<65 years, ≥65 yeas);
- sex;
- race;

ethnicity;

- nicotine use (current, former, never)
- ECOG performance at baseline (0, 1)

No formal tests of statistical significance will be performed on the demographic and baseline data.

5.4.2 Medical History

Medical history will be coded using the MedDRA version 25.0 (or a later version if updated during the study).

All medical history will be summarized by treatment group and overall in analysis set(s) applicable. Number and percentage of patients with any medical history will be reported, together with the number of patients with at least one medical history within each MedDRA system organ class (SOC) and preferred term (PT).

All the medical history reported will be listed in the individual data listing.

5.4.3 Prior and Concomitant Medication

Prior and concomitant medications received by patients will be coded using the WHODrug Dictionary version Mar2022 (or a later version if updated during the study), Anatomical Therapeutic Chemical (ATC) Classification codes.

Prior medications and concomitant medications are defined as follows:

Prior medications are those taken prior to the first dose date of investigational product.

Concomitant medications are those administrated during the period from the first dose date of investigational product, till 28 days after the last dose date. i.e., the medications with a start date on or after the first dose date of the investigational product and no later than 28 days after the last dose date; or those with a start date before the first dose date of the investigational product and a stop date on or after the first dose date of the investigational product or ongoing at the end of study.

If a medication cannot be classified as prior or concomitant after applying imputation rules for missing/incomplete dates (see Section 7.2), it will be classified as both prior and concomitant.

Prior medications and concomitant medications will be summarized separately by treatment group and overall in the analysis set(s) applicable. The number and percentage of patients using any medication will be displayed together with the number and percentage of patients using at least one medication within each therapeutic class (ATC-Level 2) and preferred name.

Prior medications and concomitant medications will be listed together in the individual data listing, with the flags for prior or concomitant medication.

Version Number: Final 2.0 Drug Substance: DZD9008

Protocol Number: DZ2019E0001 (Part B) Version Date: 16 Nov 2023

5.4.4 **Tumor Characteristics**

Variables below regarding tumor (NSCLC) characteristics will be summarized by treatment and overall in analysis set(s) applicable.

time since initial diagnosis of primary tumor to baseline (months), calculated as the (first dose date of DZD9008- initial diagnosis date of primary tumor+1)/30.4375.

If the diagnosis date is missing/partial, the time will be missing.

- histology type
- extent of disease upon entry to study (metastatic, locally advanced)

Patients with both metastatic and locally advanced site will be reported as metastatic.

- Number of organs/sites with tumor upon entry to study
- brain metastasis at baseline (Yes, No)

The brain metastasis will be derived based on extent of disease data upon entry to study.

mutation subtype

The NSCLC history data will also be listed in the individual data listing, including the extent of disease upon entry to study with the associated sites.

5.4.5 **Prior Anti-Cancer Therapy**

Variables below regarding prior anti-cancer therapy will be summarized by treatment and overall in analysis set(s) applicable.

- Any prior anti-cancer radiotherapy?
- Any prior anti-cancer systemic therapy?
- Number of regimens (as categorical variable) for prior anti-cancer systemic therapy
- Number of regimens subgroup (<3, 3)
- Categories of prior anti-cancer systemic therapy

Number and percentage of patients with each category of prior anti-cancer systemic therapy will be reported respectively. If patient had multiple medication categories, the same patient will be counted once under each category.

• Failure reason for the last line of prior platinum-based chemotherapy

The prior anti-cancer systemic therapy will be coded using the WHODrug Dictionary version Mar2022 (or a later version if updated during the study). The number and percentage of patients using at least one medication within each therapeutic class (ATC-Level 2) and preferred name will be reported in the analysis sets applicable.

The detailed data for prior anti-cancer therapy and the subsequent anti-cancer therapy will be listed in the individual data listings.

5.5 Extent of Exposure

The extent of exposure data will be listed and summarized by treatment group in the safety set. If 10% or higher difference in number of patients is observed between analysis sets, the tables can be repeated in other analysis sets (e.g., FAS).

The descriptive statistics will be provided for treatment duration, the number and percentage of patients with treatment duration in the following categories will also be reported:

- <3 months;
- 3-<6 months;
- 6-<9 months;
- 9-<12 months;
- > 12 months.

The cumulative dose, ADI and RDI during treatment period will be summarized descriptively in the safety analysis set. A categorical summary of RDI (<80%, 80-100%, >100%) will also be performed.

Number and percentage of patients with at least one dose reduction or treatment interruption will be reported, respectively.

5.6 Efficacy

[figure not shown]
Unless otherwise specified, the primary analysis population for efficacy in part B will be FAS.

To support the approval of companion diagnosis device, efficacy data analysis will be performed in centrally confirmed EGFR Exon20ins by tumor tissue analysis set. More details will be described in separate SAPs.

Similaly, centrally confirmed EGFR Exon20ins by plasma ctDNA analysis set will also be utilized to support the companion diagnosis by ctDNA.

5.6.1 Primary Efficacy Analysis

The primary endpoint for Part B of study is ORR according to RECIST 1.1 by IRC, where confirmation of response is required. The definition and derivation of ORR can be found in Section 4.2.1.

• 300 mg

P value for the test against the null hypothesis of ORR will reported based on the Simon's two-stage method. ORR and two-sided 97.5% CI will be calculated based on Jung's method [4] to adjust the bias caused by optional sampling in the Simon's two-stage design. Jung's method will provide the uniformly minimum variance unbiased estimator of ORR and CI based on binomial distribution.

• 200 mg

P value in this cohort will be calculated based on binomial exact test and the 97.5% CI of ORR will be calculated using the exact (Clopper - Pearson) method. These statistics will be considered as descriptive.

The number (%) of patients with best overall response will also be provided in the following categories: CR, PR, SD, PD and NE.

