- 5) Section 4.1.2.1: added inclusion criteria for Part A dose expansion cohort 6.
- 6) Section 4.1.2.2: removed treatment naïve from the patient population of Part B extension.
- 7) Added Table 3 to show the representative of dose intervention or modification. Updated the table listing.
- 8) Section 5.3 and 6.3.1: safety follow up period was updated from 14 days to 28 days.
- 9) Section 5.3.3: updated the interim analysis by adding futility analysis for Part B.
- 10) Section 6.9: added the EQ-5D-5L collection.
- 11) Section 7.2.2: updated the sample size calculation of Part B. Subjects will be randomized into two different dose cohorts. Each dose cohort uses a Simon two-stage design, and a sample size of 103 in each dose cohort is required to test a mull hypothesis of H₀: ORR \leq 0.17 versus an alternative hypothesis of H₁: ORR \geq 0.3 with a one-sided significance level of 0.0125 and 80% power.
- 12) Section 7.6: new added section to describe the calculation of derivation for EORTC QLQ-C30 and QLQ-LC13.
- 13) Section 7.7: new added section to describe the calculation of EQ-5D-5L.
- 14) Table 14 (study plan of Part A expansion): removed survival follow up from table to keep consistent with study objectives and assessment description.
- 15) Appendix J: added EQ-5D-5L.

Version 7.0, April 6, 2021

Summary of major changes from previous version:

- 1) Section 3.2.1 and section 5.1: updated the definition of low-fat meal (the low-fat meal is defined as approximately 400 to 500 Kcal with about 25% of calories comes from 11-14 grams of fat) to keep it consistent with FDA guidance.
- 2) Appendix J: corrected the typing of answer to question of Nausea of CTCAE PRO

Version 6.0, March 5, 2021

Summary of major changes from previous version:

1) Updated study flow chart: In the Part A expansion cohort, added cohorts dosing with DZD9008 at 200 mg and 300 mg, respectively, with low-fat meal (cohort 3 and 4) and treatment naïve cohort (cohort 5). The 200 mg and 300 mg expansion cohorts dosing

Edition Number: 12.0 Date: July 24,2023

under fasted condition in the previous flow chart (CSP version 4.0 and 5.0) are now the expansion cohort 1 and cohort 2.

- 2) Updated clinical data, including exposure, PK, safety and efficacy using new cut-off date of February 5, 2021 in section 2.3.5. Updated preliminary PK data from food effect cohort (high-fat meal).
- 3) Updated study objectives for Part A in section 1.1.1

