5.3.3 Interim analysis

An interim data analysis will take place when the last evaluable patient in Part A escalation completes the 28-day continuous dosing (DLT phase) with DZD9008 and finishes all the safety evaluation. Data analysis will be performed and a SRC meeting will be held with the decision of RP2D.

To check futility and also inform the dose selection, one interim analysis will be performed in Part B when 39 patients in full analysis set completed at least 2 RECIST assessments in each cohort. If the number of responses is less than or equal to 7 out of 39 patients in the first stage, then the dose cohort will be stopped. A dose cohort passing the first stage is considered as a "competitive" cohort. When both dose cohorts become competitive, the response rate of two cohorts will be compared to identify the more effective dose. The less effective dose may be dropped after the interim analysis.

Dizal may trigger the discussion with regulatory on the optimal RP2D selection upon emerging efficacy and safety data before interim analysis.

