7.9.7.1 Tumor response

The analysis population will be the evaluable for response analysis set for Part A and FAS for Part B.

Summaries of the number of patients with best overall response in each part will be provided in the following categories: Complete Response (CR), Partial Response (PR), Stable Disease (SD), Progressive Disease (PD) and Non-Evaluable (NE). Objective response rate and disease control rate will be summarized.

For Part B, p value for the test against the null hypothesis of ORR \le 17\% will reported based on the Simon's two-stage method. ORR and two-sided 97.5\% CI will be calculated based on Jung's method (26) to adjust the bias caused by optional sampling in the Simon's two-stage design and provide the uniformly minimum variance unbiased estimator.

Date: July 24,2023

Data will be analyzed by subgroup (e.g. taken into consideration of the prior treatment) in Part B.

7.9.7.2 **Duration of response**

The analysis population for duration of response will be the subset of the evaluable for response population (Part A) or FAS (Part B) with a best overall response of confirmed CR/PR. Duration of response will be summarized and the number (%) of responding patients with a duration of response > 3, > 6, > 9 and > 12 months will be presented. Or if data are appropriate, response ongoing rates at 6, 9 and 12 months will be estimated based on Kaplan-Meier method. A Kaplan Meier plot and median duration of response (calculated from the Kaplan-Meier) will be presented.

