2.4 Determination of Sample Size

In Part B, patients will be randomized into one of the two dose arms. Each dose arm uses a Simon two-stage design.

Bonferroni method is employed to control the family-wise type I error. The analysis in two arms will be performed independently, at one-sided significance level of 0.0125.

The primary endpoint will be ORR by IRC. Under a Simon two-stage design, a sample size of 103 within each arm is required to test a null hypothesis of ORR at one-sided significance level of 0.0125, with expected ORR of 0.3 and the null hypothesis refers to real world data of 2nd line chemotherapy for NSCLC patients with EGFR Exon20ins [2-3].

In the first stage, patients will be enrolled in each arm. If the number of responses is less than or equal to out of patients in the first stage then the arm will be stopped. If the arm proceeds to the second stage, additional patients will be enrolled to reach a total of 103 patients. If or more responses are observed, then the null hypothesis is rejected in this arm.

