6. INTERIM ANALYSES

To check futility and also inform the dose selection, one interim analysis will be performed when patients completed at least 2 RECIST assessments in each arm.

If the number of responses is less than or equal to \blacksquare out of \blacksquare patients in the first stage, then the arm will be stopped. A dose arm passing the first stage is considered as a "competitive" arm. When both dose arms become competitive, the response rate of two arms will be compared using stage 1 data to identify the more effective arm. $Pr(P_A \ge P_B| \text{ observation})$, defined as probability of true ORR in arm A higher or equal to arm B given the observation at stage 1 assuming a beta (1,1) prior distribution for both cohorts, is used to determine the

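### SAP 5.6.1 calls the 300 mg ORR estimate unbiased; that covers the futility stop, but not a dose choice made on the same Part B responses

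*SAP*

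**What the plan says.** SAP 5.6.1 reports the 300 mg ORR with a two-sided 97.5% CI by Jung's method. It gives the purpose as correcting the bias from optional sampling in the two-stage design, and adds that the method "will provide the uniformly minimum variance unbiased estimator of ORR and CI based on binomial distribution". The 200 mg results are exact binomial and descriptive.

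SAP 6 plans that, when both arms pass stage 1, "the response rate of two arms will be compared using stage 1 data to identify the more effective arm"; SAP 2.2 says the same. Protocol 5.3.3 adds: "The less effective dose may be dropped after the interim analysis". It also lets the sponsor open the dose discussion with regulators before the interim analysis, on emerging efficacy and safety data.

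SAP 1 lists a memo on dropping a dose, dated July 27, 2023, among its source documents. The SAP itself is dated 16 Nov 2023.

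No section removes the stage-1 patients from the 300 mg estimate, and none mentions bias from the dose choice.

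**The concern.** Jung's estimator is unbiased for a design with one adaptation, the stop for futility in a single arm. Part B may contain a second one: the two arms are compared and one is kept. If the comparison used responses that are also counted in the final ORR, a favourable chance result in the kept arm helps it to be kept and then enters its estimate. The estimator makes no allowance for that.

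The protocol introduction says that Part B is meant to support an accelerated approval submission. The 300 mg ORR and its CI are therefore the headline result and will be read against external benchmarks. Described as unbiased without qualification, the figure may claim more than the design supports.

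**Working it through.** **Inputs from the documents**
- Sample size and alpha: "a sample size of 103 within each arm is required to test a null hypothesis of ORR at one-sided significance level of 0.0125" (SAP 2.4).
- Null ORR 0.17 (protocol 7.9.7.1). Alternative: "with expected ORR of 0.3" (SAP 2.4).
- Futility bound: the arm stops "If the number of responses is less than or equal to 7 out of 39 patients in the first stage" (protocol 5.3.3).
- Power: 80%, given only in the protocol's summary of changes for version 8.0 ("with a one-sided significance level of 0.0125 and 80% power").

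**Assumptions, not in the documents**
- True ORRs of 30 to 50% at 300 mg, with the dose gaps shown in the table.
- Both arms pass stage 1, the arm with more stage-1 responses is kept, and ties are split at random.

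**Step 1: reproduce the design.** Take 39 patients in stage 1, stop at 7 or fewer responses, and 103 in total. Rejecting at 27 or more responses gives an exact one-sided alpha of 0.0111 and power of 0.801. Rejecting at 26 or more would give alpha 0.0196. So 103 per arm reproduces. The bound of 27 is derived here, because the SAP text as supplied leaves it blank.

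**Step 2: check the estimator without a dose choice.** For an arm that reaches stage 2 with t responses in total,

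U(t) = Σ C(38, x−1)·C(64, t−x) / Σ C(39, x)·C(64, t−x), summed over x ≥ 8.

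For an arm that stops, the estimate is x/39. The exact mean equals the true ORR at 0.17, 0.30 and 0.45. The SAP's statement is therefore correct for the two-stage stop alone.

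**Step 3: add the dose choice.** Bias = E[U(t) | both arms pass and 300 mg is kept] − true 300 mg ORR, by exact enumeration:

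| True ORR, 300 mg / 200 mg | Bias, points |
|---|---|
| 30% / 30% | +2.2 |
| 35% / 35% | +1.8 |
| 40% / 40% | +1.7 |
| 45% / 45% | +1.7 |
| 50% / 50% | +1.7 |
| 50% / 40% | +0.7 |
| 45% / 35% | +0.7 |
| 50% / 30% | +0.2 |
| 40% / 45% | +2.3 |

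Conditioning one arm on passing futility, with no dose choice, already gives about +1.0 at 30% but under 0.1 at 40%. At 30%, then, about 1 point of the 2.2 comes from the futility condition. At 40% and above almost all of the bias comes from the dose choice.

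**Step 4: hand check at 40% / 40%.** The stage-1 ORR has SD √(0.40 × 0.60 / 39) = 0.078. The larger of two independent normal values exceeds their common mean by SD/√π, here 0.078 × 0.564 = 0.044. Stage 1 carries weight 39/103 = 0.379, so the bias is about 0.044 × 0.379 = 0.017, or 1.7 points. This agrees with the enumeration.

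**Step 5: vary the rule.** SAP 6 uses Pr(PA ≥ PB) with beta(1,1) priors, but its cut-off is not visible. By simulation:
- A cut-off of 0.8 gives +3.0 to +3.7 for equal ORRs of 30 to 45%, and +1.6 to +1.7 for a 10-point advantage (45% / 35%, 50% / 40%).
- Choosing earlier, on 10 to 30 patients per arm, gives +0.8 to +1.9 for equal ORRs of 30 to 45%.
- If Part B responses play no part in the choice, the bias is zero.

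**Step 6: scale.** At an ORR of 40% the standard error with 103 patients is √(0.40 × 0.60 / 103) = 0.048, or 4.8 points. A bias of 1.7 points is about 0.35 of that.

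**The case against.** A reader might infer that the plan makes the 300 mg ORR biased by 1 to 2 points as a matter of fact. The documents do not support that. Dropping a dose is optional. The protocol also allows an earlier choice on efficacy and safety data. A memo on the dose drop predates the SAP, and its basis is not stated. The selection cut-off cannot be read. The size therefore depends on an assumed rule and assumed true ORRs. Averages over whichever dose wins, such as +1.5 points at 45% and 40%, are not figures for 300 mg; for 300 mg when it is the better and kept arm, the value there is about +1.15.

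A reader might also infer that the SAP's sentence is false. The sentence before it limits the purpose to optional sampling in the two-stage design, and for that purpose it is right (step 2). The fault is a missing qualification.

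Nor is the test compromised. SAP 5.6.5 splits the one-sided 0.025 into 0.0125 per arm, which covers testing either dose.

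These points limit the finding but do not remove it. An earlier choice also biases the estimate if Part B responses contributed (step 5), and neither document says whether they did.

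**Conclusion.** The point holds as a conditional gap of minor severity. Jung's estimate is unbiased for the futility stop only. If Part B responses that are also in the primary estimate informed the choice of 300 mg, its ORR is biased upward and its CI is shifted, and the SAP neither says so nor corrects it.

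Under the higher-count rule with both arms passing, the bias ranges from about +0.2 to about +2.3 points over the tabulated scenarios. It is largest when the doses are similar or 300 mg is slightly worse, and smallest when 300 mg is clearly better. A strict cut-off would make it larger. In the tabulated scenarios it stays below half a standard error, so it is unlikely to overturn a clear result. It does change what the headline figure can be said to be.

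**What to change.** 1. In SAP 5.6.1, limit the unbiasedness statement to the two-stage futility stop.
2. State in the SAP the data cut and the basis of the dose decision, including whether Part B responses were used.
3. If they were, report one sensitivity estimate beside Jung's. There are two options:
   - The ORR in 300 mg patients whose responses were not part of the dose-decision data. If the decision used the 39 stage-1 patients, this is at most 103 − 39 = 64. It is fewer if limited to patients enrolled after the data cut, because the interim waits for two RECIST assessments (Cycle 3 Day 1, then 6 weeks later) and no enrolment pause is stated.
   - A selection-adjusted conditional estimate using all 300 mg patients.

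The primary test stays as it is. The cost is a few sentences and one line in the primary table. The sensitivity estimate is less precise: with 64 patients at an ORR of 40% the standard error is √(0.40 × 0.60 / 64) = 0.061, or 6.1 points against 4.8. Patients enrolled after the decision were also not randomised, so they may differ from the stage-1 patients.
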